5.3 Treatment Plan

The treatment regimen and schedule are as follows:

Induction phase:

Agent	Dose	Route	Schedule
Ublituximab	900 mg	IV	Cycle 1 : Day 1, Day 8, and Day 15 Cycles 2-6 : Day 1
Acalabrutinib	100 mg - Twice daily	Orally	Every day of each cycle
Umbralisib	800 mg - Once daily	Orally	Cycle 1 : Days 1-14 Cycles 2-6 : Days 1-7

Maintenance phase:

Agent	Dose	Route	Schedule
Ublituximab	900 mg	IV	Every 2 cycles (Cycles 8, 10, 12, 14, 16, 18, 20, 22, 24) , on Day 1, starting on Day 1 of Cycle 8
Acalabrutinib	100 mg - Twice daily	Orally	Every day of each cycle
Umbralisib	800 mg - Once daily	Orally	Days 1-7 of each cycle

Treatment will be administered on an *out-patient* basis (in-patient administration is allowed if deemed necessary by the Investigator).

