5.7 Follow-Up

Following completion of protocol therapy, participants will enter follow-up.

Follow-up is comprised of:

- **Safety Follow-up**- 30 days post-last dose of protocol therapy.
 - **Note** the period for safety follow-up will be extended until stabilization or resolution for all reportable AEs (per the agreement of the Study PI) and accompanying follow-up safety report.
- **Response Follow-up**- for those who have yet to have disease progression and have not initiated a new anti-lymphoma therapy.

- **Survival Follow-up**- for all participants who have progressed OR completed Active Response Follow-Up OR initiated a new anti-lymphoma therapy. It will entail (a) Disease status (for those who have yet to progress) (b) Vital status (all participants).

Assessment time points and windows are detailed in [Section 10](#).

Note: if a participant continues therapy beyond 25 cycles with acalabrutinib for a total of 6 years of protocol therapy, the participant will only proceed with the safety follow-up visit; there will be no response/survival follow-up.

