Correlative tumor tissue ^v	X ⁿ										X ^o					
Bone marrow biopsy/ aspirate ^{p, v}	X										X					

- a. Screening activities to occur within 28 days prior to start of protocol therapy except for laboratory assessments.
- b. In the absence of treatment delay, each treatment cycle lasts 28 ± 3 days during Induction, and 28 ± 7 days during Maintenance.
- c. Maintenance phase for participants with stable disease or better response (PR or CR) at the end of Induction therapy.
- d. Activities to be performed within 72 hours prior to study drug administration.
- e. The Safety 30 days post-last dose assessments to occur 30 (± 7) days post-last dose or, if > 30 days elapsed since last dose, within 7 days after decision to end treatment. Expedited reporting will occur during this period. Safety follow-up may be extended until resolution/ stabilization of reportable AEs.
- f. For participants yet to progress, Active Follow-up will occur at 6, 12, 18 and 24 months (± 30 days for all) from last on-treatment scan until disease progression or the initiation of a new anti-lymphoma therapy.
- g. Participants who end Active Follow-up will enter Survival Follow-up. Survival assessment to occur bi-annually or as requested by the Study PI via medical record review, review of social security registry, or telephone call.
- h. *Standard physical exam* includes weight.
- i. *Vital signs*: heart rate, blood pressure, respiration rate, and temperature.
- j. *Women of childbearing potential*: Pregnancy serum test. For the screening time point, serum pregnancy test must be performed within 3 days prior to start of protocol therapy.
- k. *Screening laboratory assessments* to be performed within 14 days prior to start of protocol therapy.
- l. *Serum chemistry panel* to include: glucose, Blood Urea Nitrogen (BUN), creatinine, uric acid, total protein, albumin, magnesium, bicarbonate, calcium, inorganic phosphorous, sodium, potassium, chloride, total bilirubin, alkaline phosphatase, ALT, AST, and LDH.
- m. Correlative blood will also be collected at time of relapse. Refer to [Section 9.1.3](#) for additional information.

- n. Archival tumor tissue to be submitted post-enrollment when available. Refer to [Section 9.1.1](#).
- o. If safe and feasible, submission of left-over tissue from a standard of care tumor biopsy (fresh core or excisional biopsy) for participants who progress/relapse during study is encouraged. Refer to [Section 9.1.1](#).

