- p. Bone marrow biopsies will be performed at the following time points if feasible (please contact Study PI if bone marrow collection is not feasible at either time point to receive a waiver):
 - 1- At baseline** (during screening). If a patient had a recent bone marrow biopsy (within 90 days), this time point may be omitted after a discussion with the Study PI. In this case, a correlative sample will not be submitted.
 - 2- At the time a CR is suspected** based on imaging results (within 8 weeks after such result).
 - 3- At the time of disease relapse.**
- At each time point, bone marrow samples will be collected for correlative studies ([Section 9.1.2](#)).
- q. Every other cycle starting on C8D1 (i.e. on days of ublituximab infusion).
- r. Ublituximab infusions are on Day 1 of C8, C10, C12, C14, C16, C18, C20, C22, C24, C26, C28, and C30.
- s. Disease assessments (imaging) to occur on Days 1 (\pm 7 days).
- t. PET-CT is strongly preferred. CT in lieu of PET-CT is allowed if patient is in CR and CR was already confirmed by PET-CT, and for patients for whom PET-CT is not feasible (with Study PI's approval).
- u. Every 6 months (+/- 2 weeks) from last on treatment scan until end of protocol therapy.
- v. NGS panel (HopeSeq at City of Hope), FISH analysis, conventional cytogenetics and IHC should be performed on tumor diagnostic material (lymph node, bone marrow, peripheral blood) based on disease characteristics, per institutional practice standards at screening. Every effort should be made to collect such data ([Section 9.3](#)).
- w. Serum virology to include HBsAg, HBc antibody, HCV antibody and CMV IgG and IgM (or may do CMV by PCR at investigator discretion). If HBc antibody, HCV antibody or CMV IgG or IgM is positive, subject must be evaluated for the presence of active HBV, HCV or CMV by PCR.
- x. CMV screening by PCR for all subjects receiving study treatment beginning in Cycle 4 and approximately every 3 to 4 cycles thereafter aligned with study visits.
- y. This time point serves as TLS assessment. TLS assessment will be performed on Day 2 (+ 1 day).
- z. Activities to be performed on D15 +/- 3 days.

* EOM = End of maintenance. Visit to occur at the end of Cycle 25 (with a +7 days window) and to include disease assessment (imaging).

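### For patients who continue acalabrutinib, the calendar schedules no AE, exam or laboratory check between C24D1 and six months after the end-of-maintenance scan

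*Combined protocol and SAP*

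**What the plan says.** - **Safety visit.** Section 5.7 defines Safety Follow-up as "30 days post-last dose of protocol therapy". Study Calendar footnote e says: "The Safety 30 days post-last dose assessments to occur 30 (± 7) days post-last dose". Neither is tied to a particular agent.
- **Continuation counts as protocol therapy.** The note closing Section 5.7 covers the case "if a participant continues therapy beyond 25 cycles with acalabrutinib for a total of 6 years of protocol therapy", so acalabrutinib after Cycle 25 postpones the last dose from which the visit is counted.
- **Last doses of the other two agents.** In Section 5.3, Maintenance ublituximab is given "Every 2 cycles (Cycles 8, 10, 12, 14, 16, 18, 20, 22, 24", so it ends at C24D1. Umbralisib is given on "Days 1-7 of each cycle", so its last day is C25D7.
- **Maintenance safety checks.** Footnote q, which governs the exam, con-med, AE, CBC and chemistry rows, reads: "Every other cycle starting on C8D1 (i.e. on days of ublituximab infusion".
- **EOM visit.** The note under the calendar reads: "Visit to occur at the end of Cycle 25 (with a +7 days window) and to include disease assessment (imaging". Section 9.1.3 adds research blood. The exam, con-med, AE, CBC and chemistry rows carry no EOM mark; the PET-CT row does.
- **Continuation checks.** The next marks in those safety rows carry footnote u: "Every 6 months (+/- 2 weeks) from last on treatment scan until end of protocol therapy".

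**The concern.** The last scheduled Maintenance check comes before the final ublituximab infusion and before the umbralisib courses of C24 and C25. A patient who stops all treatment at the end of C25 has the 30-day visit soon afterwards. A patient who continues acalabrutinib does not, because the visit follows the last drug to stop. At EOM that patient attends for a scan and research blood, but the calendar asks for no AE review or routine laboratory test.

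Toxicity is a secondary endpoint. Section 11.3 wants onset date, duration, reversibility and the extreme laboratory values. Section 12.5 summarizes the toxicity of Induction and of Maintenance. For the last two Maintenance cycles of continuing patients, those laboratory extremes would rest on tests that nobody has scheduled, and low-grade events on recall months later. Section 7.1 says transaminase elevation could come from either oral agent, so a late first look during continued acalabrutinib also makes attribution harder.

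**Working it through.** The documents state no length for this interval, so there is no plan figure to reproduce. The check is calendar arithmetic.

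**Inputs**
- Maintenance cycle: 28 days, ±7 (Section 5.2).
- Last safety check under Section 5.3 and footnote q: C24D1, done within 72 hours before dosing (footnote d).
- Last ublituximab: C24D1. Last umbralisib: C25D7 (Section 5.3).
- EOM: end of C25, +7 days (EOM note).
- First continuation check: 6 months ±14 days after the last on-treatment scan, taken as the EOM scan (footnote u). Six months = 6 × 365.25/12 = 182.6 days.

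**Last check, and last ublituximab dose, to next check**
- C24D1 to end of C25: 2 × 28 = 56 days.
- C24D1 to first continuation check: 56 + 182.6 = 238.6 days, or 7.8 months.
- With the EOM and footnote u windows: 56 + 182.6 − 14 = 224.6, to 56 + 7 + 182.6 + 14 = 259.6 days.
- Adding the cycle windows and the 72-hour pre-dose window: 2 × 21 + 182.6 − 14 = 210.6, to 2 × 35 + 7 + 182.6 + 14 + 3 = 276.6 days.

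**Last umbralisib dose to next check**
- C25D7 to C25D28: 21 days.
- To first continuation check: 21 + 182.6 = 203.6 days, or 6.7 months.

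**Comparison: all drugs stopped at the end of C25**
- C24D1 to safety visit: 56 + 30 = 86 days.
- Last umbralisib to safety visit: 21 + 30 = 51 days.

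**With the safety rows marked at EOM**
- C24D1 to EOM: 56 days. EOM to first continuation check: 182.6 days.
- Last umbralisib to EOM: 21 days, or 28 with the +7-day window.

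**Dependence on the ublituximab schedule**
- Footnote r also lists infusions at C26, C28 and C30, and footnote q puts the checks on infusion days. Read literally, checks would continue to C30D1, which is 4 × 28 = 112 days after the nominal EOM. The interval to the first continuation check would then be 182.6 − 112 = 70.6 days.
- That reading conflicts with Section 5.3 and with the calendar column, which ends at C25. The 239 days therefore hold under Section 5.3 and not under footnote r.

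**The case against.** The strongest reply is that a reader might infer these patients have no safety visit and go unassessed for nearly eight months. The documents do not support that.

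- AEs are collected from consent to the end of participation and entered by cycle (Section 14.4). All SAEs are expedited throughout treatment (Section 14.5), and the listed toxicities in Section 12.4.2 are monitored throughout study treatment. Drug diaries record side effects, and the calendar lets any assessment be made more often when clinically indicated.
- EOM is an attended visit, and its note is not exhaustive: research blood is drawn there although the note does not mention it. A site may well ask about AEs.
- Infusion reactions to the last ublituximab dose would be seen in clinic on the day.
- Because events are recorded by cycle and with onset date, a C24 or C25 event that is reported can still be assigned to Maintenance.
- Of the 239 days, 183 are the interval chosen for acalabrutinib alone. Comparing 239 with the 56-day Maintenance interval mixes two phases.
- The 30-day visit is postponed, not cancelled.
- Parts of the calendar table are visibly out of alignment in its text form, for example the correlative-blood row, so a blank cell alone is weak evidence.

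Most of this stands and limits the harm. The last point carries less weight. The safety rows line up with their headings, with the footnote u mark under continuation and the next mark under the 30-day visit, and they are blank at EOM. Continuous collection also does not create a laboratory value. Footnote x asks for CMV PCR every 3 to 4 cycles, aligned with study visits, but EOM is the only visit scheduled in this interval and a PCR is not a blood count or chemistry panel. The plan already uses agent-specific limits for pregnancy reporting, including 30 days after the last ublituximab or umbralisib dose (Section 14.5), so such a limit is not foreign to it.

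**Conclusion.** The point holds as a narrow gap in scheduled safety data. For patients continuing acalabrutinib, no AE, exam, CBC or chemistry assessment is scheduled for about 239 days from C24D1 (225 to 260 with the EOM and continuation windows), or about 204 days from the last umbralisib dose. What is at risk is mainly silent laboratory changes and lower-grade events after the final ublituximab and umbralisib doses. Serious or symptomatic events would probably be captured. The primary CR endpoint and the sample size are untouched.

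This rests on three assumptions: the Section 5.3 ublituximab schedule, acalabrutinib as the only agent after Cycle 25, and the EOM scan as the last on-treatment scan. The second needs confirming, because a parenthesis in Section 12.1 refers to oral agents in the plural after 25 cycles while Sections 2.3 and 5.1 and the calendar name acalabrutinib. The documents do not say how many patients are expected to continue, so the number affected is unknown.

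**What to change.** - In the Study Calendar, mark AE assessment, con-med review, physical exam, CBC and serum chemistry at the existing EOM visit.
- In Sections 5.7 and 12.5, state that for patients continuing acalabrutinib, events up to EOM are captured at that visit and reported under Maintenance.
- Separately, reconcile footnote r with Section 5.3 on ublituximab after C24, because footnote q ties the checks to infusion days. Reconcile Section 12.1 with the other sections on which agents may continue.

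The cost is one routine laboratory panel and one AE review per patient, at a visit already attended for imaging and research blood. The change concerns data capture only and sets no dose or treatment rule. It leaves the 183-day continuation interval as it is. EOM falls 21 to 28 days after the last umbralisib dose at nominal cycle length, and 56 to 63 days after the last ublituximab infusion, so it comes close to a 30-day check for umbralisib and is later than one for ublituximab.

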11.0 ENDPOINT DEFINITIONS/MEASUREMENT OF EFFECT

11.1 Assessment of Response

Lymphoma response/progression will be evaluated using 2014 Lugano Classification (see [Appendix C](#)). [51]

Disease assessment will be performed by PET-CT. In patients in whom PET-CT is not feasible, CTs may be used in place of a PET-CT after discussion with the Study PI ([name]). Patients must have a bone marrow biopsy performed at baseline and to confirm CR (if suspected based on imaging). After CR, additional bone marrow biopsy is only required if clinically indicated and at relapse. Additional necessary restaging studies including dedicated CT scans or MRI, are permitted at the investigator's discretion. PET-CT and CT results will be read by a radiologist at each study site and investigator response assessment will be performed.

For patients with progression of disease on imaging, it is strongly recommended that a confirmatory biopsy be obtained whenever possible.

11.2 Primary Endpoint(s)

Complete response (CR) rate: defined as the proportion of response-evaluable participants (see [Section 12.2](#)) that achieve a CR at the end of induction therapy. If a patient achieves CR earlier during induction therapy but is PD at the end of induction, the patient will be considered end of induction non-CR. If a patient achieves a CR earlier during induction but does not have a response evaluation at the end of induction for some reason (for example early termination of induction due to patient refusal), the prior CR will be carried over as the end of induction CR.

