5.6 Duration of Therapy and Criteria for Removal from Protocol Therapy

Participants will receive protocol therapy until one of the below criteria are met:

- Confirmed Disease progression per 2014 Lugano classification
- Completed protocol therapy
- Participant is deemed intolerant to protocol therapy because of toxicity, despite dose modification/delay
 - **Note:** If one agent is discontinued due to toxicity, then the participant may continue to receive the other study agents
- General or specific changes in the patient's condition which render the patient unacceptable for further treatment in the judgment of the investigator
- Withdrawal of consent for further protocol therapy (See [Section 17.5](#))

Once participants meet criteria for removal from protocol therapy, the participant should then proceed to follow-up assessments ([Section 5.7](#)).

Documentation of the reason for discontinuing protocol therapy and the date effective should be made in the Electronic Health Record/medical record and appropriate eCRF.

The COH DCC and the Study PI should be promptly notified of the change in participant status.

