11.3 Secondary Endpoint(s)

Overall response rate (ORR): defined as the proportion of response-evaluable participants (see [Section 12.2](#)) that achieve a best response of either CR or PR during protocol therapy.

Progression-Free Survival (PFS): defined as the duration of time from start of protocol treatment to time of disease relapse/progression, start of non-protocol anti-lymphoma therapy, or death due to any cause, whichever occurs earlier. For patients who are alive and have not had disease relapse/progression at the last follow-up, it is censored at the time of last follow-up. .

Overall Survival (OS): defined as the duration of time from start of protocol treatment to time of death due to any cause. For patients who are alive at last follow-up, it will be censored at the time of last follow-up.

Duration of Response (DOR): Defined as the time from the first achievement of PR or CR to time of PD, start of non-protocol anti-lymphoma therapy, or death, whichever earlier. Patients who never achieve PR or CR during protocol therapy are excluded. Patient who has not had any of the failure events above at last follow-up is censored at the time of last follow-up.

Toxicity: Toxicity and adverse events will be recorded using the NCI CTCAE 5.0 scale. Observed toxicities will be summarized by type (organ affected or laboratory determination such as absolute neutrophil count), severity (by NCI CTCAE v5.0 and nadir or maximum values for lab measures), date of onset, duration, reversibility, and attribution.

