12.0 STATISTICAL CONSIDERATIONS

12.1 Study Design

This is a multicenter, single-arm Phase 2 study evaluating AU2 therapy for patients with previously untreated MCL. Patients will first receive 6 cycles of AU2 (acalabrutinib + umbralisib + ublituximab) induction; those who achieve SD or better response after induction will then receive 19 cycles of maintenance with the 3 agents, during which ublituximab will only be given every 2 cycles. Each cycle will be 28 days. Participants may continue therapy with acalabrutinib beyond 25 cycles of Induction + Maintenance therapy at the treating physician's discretion. Response will be evaluated just prior to C4, C7 (End of Induction), C14, C20 , EOM (end of maintenance), every 6 months thereafter until end of protocol therapy (if patient continues with oral agents only beyond 25 cycles), and at Safety visit.

The primary endpoint is complete response (CR) rate after AU2 induction therapy. Secondary endpoints include toxicities of AU2 induction and maintenance therapy, overall response rate to protocol therapy, duration of response, progression free survival, and overall survival.

The study sample size is based on the desire to discriminate a promising CR rate of 50% (alternative hypothesis) from a disappointing CR rate of 25% (null hypothesis) after AU2 induction. These response rates were chosen because 1) BR, a current standard, has been associated with an ORR of 80-90% and a CR rate of 40% [5, 7]; 2) In the phase 2 ACE-LY-004 trial in R/R MCL, treatment with acalabrutinib was associated with an ORR of 81% and a CR rate of 40% [39]. However, it is anticipated that this study will enroll a higher proportion of patients with high-risk MCL (*TP53* aberrations, CK) where BR is ineffective.

Simon's optimal two-stage design will be used. In the first stage, 9 evaluable patients will be accrued. If there are 2 or fewer CRs in these 9 patients, the study will be stopped. Otherwise, 15 additional evaluable patients will be accrued for a total of 24. The null hypothesis will be rejected and AU2 induction therapy will be considered promising if 10 or more CRs are observed in 24 evaluable patients. This design yields a 1-sided type I error rate of 0.05 and power of 0.8. When the CR rate is disappointing (25%), there is an 60% chance that the study will be terminated after the first stage.

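### Section 11.2 carries an earlier CR over for any missing end-of-induction evaluation, so a patient who dies or switches therapy first still counts as CR

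*Combined protocol and SAP*

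**What the plan says.** Section 11.2 defines the primary endpoint as the proportion of response-evaluable participants in CR at the end of induction. It then gives two special rules for a patient whose CR came earlier in induction.

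- "If a patient achieves CR earlier during induction therapy but is PD at the end of induction", the patient is non-CR.
- If the patient "does not have a response evaluation at the end of induction for some reason", then "the prior CR will be carried over as the end of induction CR". Early termination through patient refusal is given as an example, not as the limit of the rule.

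Section 12.1 places the induction response evaluations just before C4 and C7, so the carried CR would normally come from the pre-C4 evaluation. It also schedules later evaluations, ending with the words "if patient continues with oral agents only beyond 25 cycles), and at Safety visit". Note e to the Study Calendar (Section 10.0) sets the Safety visit at 30 (±7) days after the last dose or, if more than 30 days have already passed, "within 7 days after decision to end treatment".

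Section 11.3 treats death and new therapy as failures. PFS runs to relapse or progression, "start of non-protocol anti-lymphoma therapy, or death due to any cause, whichever occurs earlier". DOR runs from first response "to time of PD, start of non-protocol anti-lymphoma therapy, or death, whichever earlier".

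**The concern.** An endpoint named CR at the end of induction should not count a patient who was dead, or already on another lymphoma treatment, when induction was due to end. The pre-C4 and C7D1 evaluations are three 28-day cycles apart (3 × 28 = 84 days), which leaves time for such events. Under the carry-over rule the same patient could be a PFS and DOR failure in cycle 5 and a CR at the end of cycle 6.

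For these patients the error runs one way: it can only add CRs. Both decisions in the two-stage design can turn on one patient, 2 against 3 CRs of 9 and 9 against 10 of 24. The trial is open-label and single-arm, and response is assessed by the investigator, so the rule is best settled before a borderline case arises.

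**Working it through.** **Does another section close the gap?** Take a patient in CR before C4 who dies or switches therapy in cycle 5.

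- Section 12.2: the patient has had at least one cycle and one post-baseline evaluation, so is response-evaluable. The non-CR rule there covers only patients who, because of progression or toxicity, did not finish one cycle or stopped before any response assessment. It does not apply.
- Section 12.5: restates the proportion and its exact interval and adds no handling rule.
- Section 12.1: the Safety-visit evaluation cannot help after death, and may come after new therapy has begun. No section says that it stands in for the end-of-induction evaluation.
- Section 5.6: removal for progression requires "Confirmed Disease progression per 2014 Lugano classification", so progression will usually have been documented by an evaluation. Death and new therapy have no such safeguard.

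The carry-over rule therefore decides the case, and scores it as CR.

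**The plan's own figures.** Inputs from Section 12.1: stop at 2 or fewer CRs in 9; promising at 10 or more in 24; null rate 25%, target rate 50%. With X₁ ~ Bin(9, p) and X₂ ~ Bin(15, p):

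P(promising) = Σ over x = 3 to 9 of P(X₁ = x) × P(X₂ ≥ 10 − x)

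- p = 0.25: 0.0485 (plan: 0.05)
- p = 0.50: 0.8055 (plan: 0.8)
- P(X₁ ≤ 2) at p = 0.25: 0.6007 (plan: 60%)

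All three reproduce.

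**Effect of wrongly carried CRs.** Let q be the share of patients counted as CR only through carry-over after death or a switch. The documents give no value, so q is assumed. The counted CR rate becomes 0.25 + q.

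| q (assumed) | P(promising) | P(pass stage 1) | Expected cases in 24 (24q) | P(at least one in 24) = 1 − (1 − q)²⁴ | Share of counted CRs = q/(0.25 + q) |
|---|---|---|---|---|---|
| 0 | 0.0485 | 0.399 | 0 | 0 | 0 |
| 0.5% | 0.055 | 0.413 | 0.12 | 11% | 2.0% |
| 1% | 0.062 | 0.427 | 0.24 | 21% | 3.8% |
| 2% | 0.077 | 0.455 | 0.48 | 38% | 7.4% |

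To judge whether these values of q are plausible, suppose 20% to 40% of patients are in CR before C4 (also assumed). Then q = 0.5% means that 1.25% to 2.5% of early CRs are lost in this way (0.5/40 to 0.5/20); q = 1% means 2.5% to 5%, and q = 2% means 5% to 10%.

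**Closeness to the boundaries at p = 0.25.** P(exactly 2 of 9) = 0.300. P(pass stage 1 and end at exactly 9 of 24) = 0.052.

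**The case against.** The best defence is that the primary objective is anti-tumor activity. A documented CR, with marrow biopsy called for when CR is suspected, is evidence of activity even if the patient later dies of another cause. The rule is explicit and set in advance. ORR, the other response endpoint, uses best response and also keeps a responder who later dies or switches; PFS and DOR are time-to-event endpoints, where such events are natural failures. This is a fair argument for a best-response endpoint. It does not fit an endpoint that Section 11.2 ties to the end of induction and for which it already overturns an earlier CR when progression is found.

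The objection on weight largely stands. The cases should be rare and every rate above is assumed. At q = 0.5% and 1% the chance of declaring AU2 promising rises by only 0.006 and 0.013. The 0.300 and 0.052 are chances of sitting at a boundary, not of a wrong decision.

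A reader might infer two stronger points that the documents do not support:

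- *That progressing patients are routinely counted as CR.* Sections 5.6 and 12.1 make this case nearly empty. Progression found when induction stops early can also reasonably be read as progression at the end of induction.
- *That progression is the only outcome that undoes an earlier CR.* A C7D1 evaluation showing PR or SD is already non-CR under the main definition.

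**Conclusion.** The point holds for a narrow group: patients in CR before C4 who die, or who start non-protocol anti-lymphoma therapy without a further evaluation, before the planned C7D1 evaluation. For them the stated rule gives a definite result that does not match the endpoint's definition, and no other section corrects it. For progression, 11.2 only needs to say explicitly what 5.6 and 12.1 largely secure.

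The probable effect is small. An assumed 0.5% to 2% of patients wrongly carried moves the chance of a false positive from 0.0485 to between 0.055 and 0.077. These figures rest on the assumed rates and on a true end-of-induction CR rate of exactly 25%. They do not show an error in the design calculation, which reproduces. Low severity.

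**What to change.** Change Section 11.2 in two places.

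1. Keep the carry-over, including for refusal, withdrawal or loss to follow-up with no known failure event. Count the patient as non-CR if any of these is recorded before the planned C7D1 evaluation: death; documented progression; or start of non-protocol anti-lymphoma therapy without an intervening evaluation still showing CR.
2. State that, after early termination of induction, a Safety-visit response evaluation done before any new therapy serves as the end-of-induction evaluation. Death or documented progression before the planned C7D1 date still counts as non-CR.

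Naming recorded events matters. A rule requiring every carried patient to be known alive and progression-free at C7D1 could turn withdrawn or lost patients into non-CR, against the protocol's own refusal example.

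The denominator, the replacement rule and the 3/9 and 10/24 thresholds do not change, and no patients, scans or visits are added.

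The cost is that the reported CR rate may be slightly lower. A CR patient who leaves for other therapy without a further evaluation becomes non-CR, while one evaluated in CR before leaving stays CR. Section 5.8 foresees patients leaving for autologous transplantation, so this can happen. If 0.5%, 1% or 2% of patients (assumed) were such cases at a true 50% CR rate, the counted rate would be 49.5%, 49% or 48%, and power 0.793, 0.780 or 0.751 instead of 0.8055. Sentence 2 limits this loss.
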